9. STATISTICAL CONSIDERATIONS AND METHODS

9.1. Sample Size Determination

A post hoc analysis was conducted using a subgroup of AUX-CC-871 subjects who were rated with moderate/severe AC based on baseline MRI images. This subgroup displayed a notable treatment effect (EN3835 vs placebo) on the pain and composite components of the adapted ASES questionnaire. This subgroup also displayed a treatment effect trend for the functional component of the adapted ASES. Given this result, the sample size calculation is based on the mean and SD found in this subgroup for the adapted ASES composite score on Day 95. Given a mean change from baseline value of 38.6 for the EN3835 group and 27.6 for the placebo group with an SD of 21.6, a sample size of approximately 142 subjects would be required given a 1:1 randomization and a type I error of 0.05 with a power of 85%. With an expected drop-out rate of approximately 20%, 180 subjects (90 EN3835 and 90 placebo) should be dosed to ensure 142 subjects complete the study.

9.2. **Populations for Analysis**

For the purposes of analysis, the following populations are defined:

- The Safety Population is defined as all randomized subjects who received at least 1 injection of study treatment (EN3835 or placebo). All safety analyses will be based on this population.
- The Intent-to-Treat (ITT) Population is defined as all randomized subjects who received at least 1 injection of study treatment (EN3835 or placebo).
- The Modified Intent-to-Treat (mITT) Population is defined as all ITT subjects who have a valid baseline adapted ASES composite score in the affected shoulder and at least 1 valid adapted ASES composite score after the injection of the study treatment. All efficacy analyses will be based on this population.
- The Per-Protocol (PP) Population is defined as those subjects in the mITT Population who do not have any major protocol deviations. Determination of PP subjects will be completed before the study database is closed and locked. If more than 10% of the mITT Population is excluded from the PP Population, then all efficacy summaries will be repeated using the PP Population for the sensitivity analysis.

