6. STATISTICAL METHODS

6.1. General Methodology

All statistical tests, summary tables and data listings will be prepared using SAS version 9.3 or higher.

All statistical tests of efficacy parameters will be 2-sided with a significance level of α =0.05, unless specified otherwise. Statistical tests will be supported by presenting estimates and 95% confidence intervals (CI) for each treatment group.

Continuous data will be summarized using descriptive statistics (number of subjects [n], mean, SD, median, minimum, and maximum). Discrete data will be summarized using frequency counts and percentages. The denominator will be based on the number of subjects in the appropriate population.

For the purpose of display, the summary results will be rounded as follows:

- Minimum and maximum: Same number of decimal places as the raw data.
- Mean and Median: One more decimal place than the raw data.

- SD: Two more decimal places than the raw data.
- Percentages will be displayed with 1 decimal place precision. A zero count will be left blank.
- The standard form of a percentage change variable is 0 decimal places.

For categorical variables with missing values, a category documenting the frequency of missing values will be displayed in the summary tables.

Summary tables, subject listings, graphs and any supportive SAS output will include footnotes that will indicate:

- Date of data extraction.
- Date and time of output generation.
- SAS program name, including the path that generated the output.

When calculating percentages, the denominator will be based on the number of subjects with non-missing values. If the denominator is expected to change over time, then the denominator used to calculate the percentage will be based on the number of subjects with non-missing values at each visit. Any subject removed from an analysis will be noted at the bottom of the table along with the reason the subject was removed.

Empty summary tables will be presented with a note stating that "No Subjects Met Criteria."

Subject listings of all data from the eCRFs as well as any derived variables will be presented.

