7.9.4. Sensitivity Analysis

7.9.4.1. Primary Endpoint Sensitivity Analysis with MMRM using Tipping Point Analysis (TPA)

A sensivity analysis will be performed to assess the impact of missing data with MMRM using tipping point analysis as described in section 7.9.1. Note that if the primary analysis result is not significant (p-value greater than 0.05), no sensitivity analysis will be performed.

To evaluate the impact of deviations from the missing at random (MAR) assumption, a deltaadjustment multiple imputation (MI) method will be used to find the tipping point where the result is no longer statistically significant.

There are three steps to be followed for this sensivity analysis.

Step 1: Generate Pattern of Missing Data

Before various MI methods are applied, the different types of missing data patterns will be checked using NIMPUTE=0 in SAS PROC MI. This will generate the pattern of missing data and will not generate any imputed values for missing data.

PROC MI DATA=*INPUT* NIMPUTE=0; VAR *VAR1 VAR2 VAR3...(variables in order the missing patterns are created for)*; RUN;

Step 2: Imputation of data for non-monotone and monotone missing data

• Intermittent missing values: If there are subjects with intermittent missing values (ie. non-monotone missing data), the intermittent missing values will be imputed based on Markov Chain Monte Carlo (MCMC) methods. SAS PROC MI will be utilized with MCMC to generate datasets with monotone missing pattern. The number of imputations will be set to *n* (20 is the default value).

PROC MI DATA=*INPUT* NIMPUTE=*n* SEED=234 OUT=*IN_MCMC*; VAR ...; (treatment group, baseline covariates, and the preceding non-missing values in the order of clinical visits: baseline, Visit X, ..., Visit Y) MCMC CHAIN=SINGLE NBITER=1000 NITER=1000 IMPUTE=MONOTONE; RUN;

- If all subjects have a monotone missing data pattern (either directly from the study or created by the previous step), the MAR-based multiple imputation with the regression option will be used to impute missing values, the imputed values will then be adjusted accordingly. Delta-adjustment will be generated for different combinations of δ_P an δ_A values as defined below:
 - Active-only adjustment analysis: $\delta_P = 0$ and $\delta_A = 0$ to Δ_1 (Δ_1 is the effect size reported in the primary analysis)
 - Analysis with a control adjustment that is half of the active adjustment: $\delta_P = \delta_A / 2$ and $\delta_A = 0$ to Δ_1

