 - All arms with identical adjustment: $\delta_P = \delta_A$ and $\delta_A = 0$ to Δ_1
- The imputation will be performed using SAS PROC MI with the MONOTONE statement and the REGRESSION option with the following specifications:

```
PROC MI DATA=IN_MCMC NIMPUTE=1 (see note) SEED=234 OUT=OUTPUT;
VAR ...; (treatment group, baseline covariates, and the preceding non-missing values in
the order of clinical visits: baseline, Visit X, ..., Visit Y)
CLASS...; (treatment group)
MONOTONE REG (/details);
MNAR ADJUST (Visit X / SHIFT=delta_a ADJUSTOBS=(TRT01PN ='1'));
MNAR ADJUST (Visit Y / SHIFT=delta_a ADJUSTOBS=(TRT01PN ='1'));
MNAR ADJUST (Visit Y / SHIFT=delta_a ADJUSTOBS=(TRT01PN ='1'));
MNAR ADJUST (Visit X / SHIFT=delta_a ADJUSTOBS=(TRT01PN ='1'));
MNAR ADJUST (Visit X / SHIFT=delta_p ADJUSTOBS=(TRT01PN ='0'));
MNAR ADJUST (Visit Y / SHIFT=delta_p ADJUSTOBS=(TRT01PN ='0'));
MNAR ADJUST (... / SHIFT=delta_p ADJUSTOBS=(TRT01PN ='0'));
```

Note: NIMPUTE=n if MCMC was NOT applied at the previous step.

Step 3: Analysis and Pooling

For each value of δ_P and δ_A , MMRM described in section 7.9.1 will be performed for each of the n adjusted fully imputed datasets. The analysis results obtained will be combined into a single estimation using PROC MIANALYZE to produce final inferences.

The following estimates will be presented in the sensitivity analysis table:

- 1. LSM estimate for the mean change from baseline at the visit where primary endpoint is measured for each treatment.
- 2. LSM estimate for treatment difference of the mean change from baseline at the visit where primary endpoint is measured and the corresponding 2-sided 95% CI and p-value for change from baseline in the primary endpoint will be provided.

Shift parameters will begin with active-only adjustment, followed by a control adjustment that is half of the active adjustment, followed by all arms with identical shift adjustments, as stated in Step 2.

25-April-2022

All steps above are repeated with different values of the shift parameter until the tipping point is reached or all possible values are explored. The tipping point can be identified when the result is no longer statistically significant (p-value >0.05). It is possible a tipping point is not reached if little to no data is missing.

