Once tipping point is reached, if implausible departure from MAR is needed to change the results from statistically significant to insignificance, the results of the primary endpoint are considered to be robust. If the tipping point obtained for overturning the primary endpoint result is clinically plausible, the conclusion can be questioned and viewed with caution.

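### The tipping-point search stops at a shift equal to the observed effect, so it can often end without a tipping point, and the SAP states no conclusion for that case

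*SAP*

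**What the plan says.** SAP 7.9.4.1 describes a delta-adjusted multiple imputation analysis whose aim is to find the shift at which the primary result loses significance. It is run only if the primary p-value is 0.05 or less. There are three schemes: EN3835 values shifted alone, placebo shifted by half as much, and both arms shifted equally. In each, the EN3835 shift runs from 0 to Delta_1, and Delta_1 "is the effect size reported in the primary analysis".

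Step 3 adds: "All steps above are repeated with different values of the shift parameter until the tipping point is reached or all possible values are explored". It refers the schemes back to Step 2, and no range beyond Delta_1 is given.

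On the outcome, the SAP notes: "It is possible a tipping point is not reached if little to no data is missing". The rule for interpretation begins "Once tipping point is reached, if implausible departure from MAR is needed" and, on that condition, ends "the results of the primary endpoint are considered to be robust". Nothing is said about a search that reaches Delta_1 without tipping.

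**The concern.** A tipping-point analysis is useful because it finds the departure from missing at random that would overturn the result, so that clinicians can judge whether that departure is plausible. The search therefore has to go far enough to find it. A shift applied only to the missing part of one arm moves the treatment difference by only a fraction of the shift. A limit equal to the effect itself can therefore leave most of the effect in place.

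This is the only sensitivity analysis for missing data that the visible SAP text specifies for the primary endpoint (SAP 6.3.1 and 7.9.4). If it ends without a tipping point, the reader gets neither a departure to judge nor a stated conclusion. The one explanation that the SAP mentions, little missing data, need not be the true one.

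**Working it through.** **Inputs.** Protocol 9.1: "Given a mean change from baseline value of 38.6 for the EN3835 group and 27.6 for the placebo group with an SD of 21.6", 1:1 allocation, type I error 0.05, power 85%, 142 evaluable, 180 dosed, dropout about 20%. SAP 6.1: tests are two-sided. SAP 4.7.1.3: the composite runs from 0 to 100 and higher is better, so a worsening shift is negative; the sizes below are absolute values. Assumption: a share m of EN3835 Day 95 scores is missing, 20% as base case. The documents give no missing rate for the mITT population.

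**The plan's own figure.** For a difference of 38.6 − 27.6 = 11.0 and SD 21.6, a two-sided t-test has 85.4% power with 71 per arm, which reproduces 142. Allowing for 20% dropout gives 142/0.8 = 178, close to 180.

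**Result at the planning effect.** SE = 21.6 × √(2/71) = 3.63; z = 11.0/3.63 = 3.03; p = 0.0024.

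**Effect of the limit (single Day 95 shift, constant SE).** A worsening of δ in a share m of the EN3835 arm lowers the difference to Delta_1 − mδ. At δ = Delta_1 it is Delta_1 × (1 − m). The active-only scheme can therefore tip only if z < 1.96/(1 − m). A result at the planning effect tips at δ = (11.0 − 1.96 × 3.63)/m.

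| m | z must be below | p must be above | Tipping shift at planning effect | Multiple of Delta_1 | Share of significant results that tip, true effect 11 |
|---|---|---|---|---|---|
| 10% | 2.18 | 0.029 | 38.9 | 3.5 | 6% |
| 20% | 2.45 | 0.014 | 19.5 | 1.8 | 16% |
| 30% | 2.80 | 0.005 | 13.0 | 1.2 | 31% |
| 40% | 3.27 | 0.001 | 9.7 | 0.9 | 53% |

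At m = 20% the half-shift scheme needs z < 1.96/(1 − 0.10) = 2.18, or p > 0.029. Equal shifts hardly move the difference when missingness is balanced.

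**What the limit tests.** On planning means, 38.6 − 11.0 = 27.6, the placebo mean. At m = 20% the tip comes at 38.6 − 19.5 = 19.1 points of improvement, which lies outside the range.

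**Carry-forward.** The SAP code applies a shift at each visit and uses earlier visits as predictors, but the text does not say whether earlier shifts feed later imputations. If they do, with an assumed visit correlation of 0.6, one earlier missed visit makes the Day 95 shift 1 + 0.6 = 1.6 times Delta_1. At m = 20% the estimate then falls to 1 − 0.2 × 1.6 = 0.68 of Delta_1, and results with p above about 0.004 can tip.

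**Simulation.** 90 per arm, four visits, monotone dropout, 20 imputations, pooled inference on the Day 95 mean difference, 300 trials per setting, m = 20%, correlation 0.6. Share of significant results that tip in the active-only scheme:

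| True effect | Shifts not carried forward | Shifts carried forward |
|---|---|---|
| 11 | 11% | 33% |
| 8 | 37% | 55% |
| 5.5 | 45% | 66% |

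At a true effect of 11, 67% to 89% do not tip. With correlations of 0.4 and 0.8 included, the range is 58% to 89%. The median tipping shift is 1.3 to 2.0 times Delta_1. The half-shift scheme tips in 2% to 14% and the equal-shift scheme in 1% to 3%.

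**The case against.** The limit has a meaning: on planning values it removes the whole drug benefit from EN3835 dropouts. Both arms are also assigned physical therapy and home exercise, which Protocol Section 8 wants continued even after withdrawal, so how far below a placebo-like response to search is partly a judgment. The results table gives the difference, confidence interval and p-value, so a reader could see how far the result at the limit is from tipping. This is a sensitivity analysis in a phase 2 trial and leaves the primary analysis unchanged. These points keep the matter in proportion, but they do not supply the missing range or the missing conclusion.

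A reader might infer four stronger things that the documents do not support.

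- **That the result is robust by construction.** The SAP calls the result robust only after a tipping point has been reached and found implausible. It is silent otherwise.
- **That failure to tip is offered as proof of little missing data.** The sentence runs the other way. It is a true caveat that little missing data may prevent tipping.
- **That most significant results can never tip.** This depends on the missing share, the true effect and carry-forward. With 40% missing at a true effect of 11, or with true effects of 8 or 5.5 and carried-forward shifts, most do tip. The p-value thresholds hold only for a single Day 95 shift and constant SE.
- **That the higher early termination behind Amendment 4 makes the limit worse.** More missing data loosens it.

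The stop rule's mention of all possible values could be read as allowing larger shifts, but no wider range is defined.

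**Conclusion.** The concern holds in a limited form. The specified range ends at Delta_1 in all three schemes, so no case is examined in which EN3835 dropouts do worse than about the placebo mean. With about 20% missing and a true effect of 11 points, roughly two thirds to nine tenths of significant results would end without a tipping point in the active-only scheme, and more in the other two. These figures rest on assumed values for the missing share, visit correlation and dropout pattern, and on a true effect taken from a post hoc subgroup. The SAP gives no conclusion for a search that does not tip, and little missing data would not explain such an outcome at 20% missing. The change should be made, but the primary analysis does not depend on it.

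**What to change.** In SAP 7.9.4.1:

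1. Define Delta_1 as the Day 95 LS mean difference in ASES points. Effect size could otherwise be read as a standardized value (11/21.6 = 0.51).
2. Extend the worsening EN3835 shift in fixed steps, for example 2 points, beyond Delta_1 until p > 0.05 or until the shift equals the EN3835 LS mean change from baseline, meaning no improvement (about 38.6 on the planning mean).
3. State whether shifts at earlier missed visits carry into later imputations.
4. Report the tipping shift in ASES points.
5. State that not tipping within the range is not by itself evidence of robustness or of little missing data, and report the estimate at the limit. This is needed even with the longer range: at 10% missing, a result at the planning effect would tip at 38.9, just past no improvement.

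The equal-shift scheme can stay; a two-way grid over both arms' shifts is optional. The cost is SAP wording and a longer loop in the same program, with no new data.

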7.9.5. Supportive Analysis

7.9.5.1. Per-Protocol Population Analysis

If more than 10% of the mITT Population is excluded from the PP Population, then select efficacy summaries will be repeated using the PP Population for the supportive analysis.

7.10. Safety Analyses

Safety data will be summarized by each treatment group and overall using the Safety Population. Subjects will be included in the safety analyses based on the actual treatment received.

7.10.1. Study Drug Exposure

The study drug exposure will be summarized at each treatment visit and by each treatment group. The following will be summarized descriptively:

- Number of injections received.
- Total dose administered (mg).

A subject listing of overall exposure will be provided.

7.10.2. Adverse Events

Proportion of subjects reporting at least 1 adverse event, treatment-emergent adverse event, adverse event of special interest, and serious adverse event will be compared for EN3835 to placebo treatment group using Fisher's exact test.

The null and alternative hypotheses for this test will be as below:

 H_0 : p1 = p2 (Proportion of subjects having an adverse event are equal in treatment groups) Vs

H₁: $p1 \neq p2$ (Proportion of subjects having an adverse event are unequal in treatment groups) Where,

p1: Proportion of subjects having adverse event in EN3835 treatment group.

p2: Proportion of subjects having adverse event in placebo treatment group.

Number and proportion of subjects with at least 1 adverse event, treatment-emergent adverse event, adverse event of special interest, and serious adverse will be summarized by treatment groups and in addition p value for treatment comparison will also be presented.

All AE summary tables will include only TEAEs, unless otherwise specified.

AEs will be summarized by SOC and PT. A subject will only be counted once per SOC and PT.

For AEs by severity grade (mild, moderate, severe), if a subject has multiple events occurring in the same SOC or same PT, then the event with the maximum intensity (ie, severe) will be counted.

For AEs by relationship to study drug, if a subject has multiple events occurring in the same SOC or same PT, the event with the highest association (ie, related) to study drug will be summarized.

AEs will be presented in decreasing order of the incidences at SOC level and within each SOC, in decreasing order of the incidences at the PT level.

An overall summary of AEs and AEs related to study drug will be presented and will include:

- Total number of TEAEs reported.
- Total number of TEAEs reported by severity.
- Total number of TEAEs of special interest.
- Subjects with any TEAE.
- Subjects with any TEAE of special interest.
- Subjects with any serious TEAE.
- Subjects with any severe TEAE.
- Subjects with no severe TEAEs, but at least 1 moderate TEAE.
- Subjects with no severe TEAEs, but at least 1 mild TEAE.
- Subjects with any TEAEs leading to drug interruption/withdrawal.
- Subjects with any TEAEs leading to study discontinuation.
- Subjects with any TEAEs resulting in death.

The following summary tables will be presented by SOC and PT:

- All TEAEs.
- Study drug related TEAEs.
- TEAEs by severity.
- Study drug related TEAEs by severity.
- Study drug related TEAEs by treatment session
- Duration (1-7 days, 8-14 days, 15-21 days, > 21 days) of study drug related TEAEs.
- Serious TEAEs.

- TEAE of special interest.
- TEAE of special interest by severity.

Most common non-serious TEAEs by order of frequency (Most frequent, 2nd most frequent, and 3rd most frequent) will be summarized by PT. Most common non-serious AEs are those that at least 5% of the subjects reported at least once (using PT).

The following listings will be presented by subject:

- All AEs.
- AEs resulting in death.
- Non-fatal serious AEs.
- AEs resulting in drug interruption/withdrawal.
- AEs resulting in study discontinuation.

Refer to Table 16 for computation of duration of AEs.

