9.3.2. Safety Analyses

All subjects who receive at least 1 dose of study treatment will be included in the safety analyses. Subjects will be included in the safety analyses based on the actual treatment received.

Treatment comparisons for safety parameters will be performed using Fisher exact tests for categorical data such as event rates or Student t test for continuous data such as changes from baseline in the laboratory tests and vital signs using type 1 error rate of 0.05.

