7.10.3. Clinical Laboratory

Student *t* test (2-sample *t* test) will be used to compare EN3835 to placebo for change from baseline in the laboratory parameters (hematology and chemistry) at the Day 95 Visit.

The null and alternative hypotheses for this test will be as below:

H₀: There is no significant difference in mean change in laboratory parameters for 2 treatment groups.

Vs

H₁: There is significant difference in mean change in laboratory parameters for 2 treatment groups.

Hematology and chemistry results will be summarized by each treatment group using descriptive statistics for observed and change from baseline values along with p value at Day 95/EOS Visit.

Proportion of subjects reporting with PCI laboratory values will be compared for EN3835 to the placebo treatment group using Fisher's exact test. Refer to Table 13 for PCI criteria.

The null and alternative hypotheses for this test will be as below:

 H_0 : p1 = p2 (Proportion of subjects having PCI laboratory values are equal in treatment groups)

Vs

 H_1 : p1 \neq p2 (Proportion of subjects having PCI laboratory values are unequal in treatment groups)

Where,

p1: Proportion of subjects having PCI laboratory values in EN3835 treatment group.

P2: Proportion of subjects having PCI laboratory values in placebo treatment group.

The PCI laboratory values will be summarized by treatment groups. In addition, the p value for treatment comparison will be presented.

A subject listing will be presented for all laboratory parameters (hematology, biochemistry, urinalysis, TSH and HbA1c). Serum and urine pregnancy test results will be listed separately.

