7.10.4. Vital Signs

Student *t* test (2-sample *t* test) will be used to compare EN3835 to placebo for change from baseline in the vital signs (SBP, DBP, pulse rate, respiratory rate, body temperature, and body weight) at Day 1, 22, 43, 64, and 95 Visits.

The null and alternative hypotheses for this test will be as below:

H₀: There is no significant difference in mean change in vital sign parameters between the 2 treatment groups.

Vs

H₁: There is a significant difference in mean change in vital sign parameters between the 2 treatment groups.

Vital signs (SBP, DBP, pulse rate, respiratory rate, body temperature) taken on the injection days will be summarized across the required measurement time points (15 minutes and 30 minutes post injection) for each treatment group using descriptive statistics for observed and change from baseline values.

Vital signs taken at each visit will be summarized across study visits not including the post injection time points for each treatment group and overall using descriptive statistics for observed and change from baseline values along with *p* value.

Proportion of subjects reporting with PCI vital sign values will be compared for EN3835 to the placebo treatment group using Fisher's exact test. Refer to Table 14 for PCI criteria.

The null and alternative hypotheses for this test will be as below:

 H_0 : p1 = p2 (Proportion of subjects having PCI vital sign values are equal in treatment groups)

Vs

 H_1 : $p1 \neq p2$ (Proportion of subjects having PCI vital sign values are unequal in treatment groups)

Where,

p1: Proportion of subjects having PCI vital sign values in EN3835 treatment group.

p2: Proportion of subjects having PCI vital sign values in placebo treatment group.

The PCI vital sign values will be summarized by treatment groups. In addition, the p value for treatment comparison will be presented.

A listing will be presented for vital signs results.

7.10.5. 12-Lead ECG

The investigator interpretation of ECG results (normal, abnormal not clinically significant, or abnormal clinically significant) will be summarized by each treatment group and overall using frequency counts and percentages.

A listing of investigator interpretation of ECG results will be presented.

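### The categorical safety comparisons end in a Fisher p value with no between-arm risk difference or confidence interval, which says little about uncommon events at about 90 per arm

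*SAP*

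**What the plan says.** Protocol 9.3.2 sets the method: "Treatment comparisons for safety parameters will be performed using Fisher exact tests for categorical data such as event rates". The same sentence assigns Student t tests to "changes from baseline in the laboratory tests and vital signs using type 1 error rate of 0.05".

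SAP 7.10.2 applies this to four categories: "Proportion of subjects reporting at least 1 adverse event, treatment-emergent adverse event, adverse event of special interest, and serious adverse event will be compared" between EN3835 and placebo by Fisher's exact test. The null is p1 = p2 and the alternative is that "Proportion of subjects having an adverse event are unequal in treatment groups", so the test is two-sided. For output, numbers and proportions "will be summarized by treatment groups and in addition p value for treatment comparison will also be presented".

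SAP 7.10.3 repeats the pattern: "Proportion of subjects reporting with PCI laboratory values will be compared for EN3835 to the placebo treatment group using Fisher's exact test". SAP 7.10.4 does so for vital signs: "Proportion of subjects reporting with PCI vital sign values will be compared for EN3835 to the placebo treatment group using Fisher's exact test". Each adds a p value to the summary by arm.

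The only general sentence on intervals is in SAP 6.1: "Statistical tests will be supported by presenting estimates and 95% confidence intervals (CI) for each treatment group". It directly follows a sentence about tests of efficacy parameters. By contrast, the efficacy MMRM sections (SAP 7.9.1.1 and 7.9.2.1 to 7.9.2.4) ask for 95% intervals on the EN3835 minus placebo difference.

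**The concern.** Safety is a stated objective of the trial, but its size was set on the adapted ASES composite score (Protocol 9.1, SAP 3.5). For uncommon events such as hypersensitivity, other AESIs, SAEs and PCI values, a test of equality at this size will often be non-significant even when EN3835 carries a real excess. The useful question is then how large an excess the data still allow. A p value does not answer it. Two separate per-arm intervals, if SAP 6.1 does reach the safety tables, do not bound the difference either. The safety tables would therefore lack the quantity that the SAP already provides for its efficacy MMRM analyses.

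**Working it through.** **1. The plan's own numbers.** Inputs from Protocol 9.1: mean changes 38.6 and 27.6 (difference 11.0), SD 21.6, alpha 0.05, power 85%, 1:1 allocation, drop-out about 20%.

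- Per arm: 2 × (1.960 + 1.036)² × 21.6² / 11.0² = 69.2, so 70, or 140 in total. The plan states 142.
- Inflation: 142 / 0.80 = 177.5, so 178. The plan states 180, 90 per arm.

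The efficacy sizing reproduces closely. No power or detectable difference is stated for safety. The Safety Population is everyone randomized and dosed, so n = 90 per arm is used below.

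**2. What Fisher needs when placebo has no events.** With equal arms and k events, all on EN3835, the two-sided p value is 2 × C(90, k) / C(180, k).

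| EN3835 vs placebo events | Calculation | p |
|---|---|---|
| 4 vs 0 | 2 × 2,555,190 / 42,296,805 | 0.121 |
| 5 vs 0 | 2 × 43,949,268 / 1,488,847,536 | 0.059 |
| 6 vs 0 | 2 × 622,614,630 / 43,424,719,800 | 0.029 |

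Six events are the minimum against none. Against 1 placebo event the minimum is 8.

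**3. What an interval would show for the same data.** The Newcombe interval combines the Wilson limits of each arm. For 4/90 the Wilson limits are 1.74% and 10.88%; for 0/90 they are 0% and 4.09%. The difference is 4.44 points.

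- Lower: 4.44 - √[(4.44 - 1.74)² + (4.09 - 0)²] = 4.44 - 4.90 = -0.5
- Upper: 4.44 + √[(10.88 - 4.44)² + (0 - 0)²] = 10.9

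So p = 0.12 goes with an excess of up to 10.9 points not excluded. For 5 vs 0 the interval is 0.4 to 12.4 points, beside p = 0.059.

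**4. How often Fisher is non-significant.** This is the exact probability that p > 0.05, summed over all 91 × 91 outcomes at 90 per arm. Every rate pair is an assumption, because the documents give no control-arm safety rates. The last column is the probability that the Newcombe 95% interval includes zero.

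| Placebo vs EN3835 (assumed) | Fisher p > 0.05 | Newcombe includes 0 |
|---|---|---|
| 1% vs 3% | 97.6% | 93.8% |
| 1% vs 5% | 84.8% | 74.3% |
| 5% vs 15% | 45.3% | 40.1% |
| 10% vs 20% | 60.3% | 53.4% |
| 5% vs 20% | 15.3% | 12.0% |
| 0% vs 10% | 10.3% | 4.7% |
| 10% vs 34.2% | 2.7% | 1.8% |

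The 34.2% in the last row is the musculoskeletal pain rate in Protocol 2.3 (treatment-related events in the earlier phase 2b study). The 10% placebo rate beside it is assumed.

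**The case against.** Several counter-arguments have force.

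- **The non-significance rates are not a property of the plan.** A reader might take the 45% to 98% seen for some rate pairs as the plan's miss rate for relevant harms. The documents do not support that. They give no control-arm rates and define no relevant excess, and other assumed pairs give 10% or 15%. The few AE rates in Protocol 2.3 include common events, for which a sizeable excess would usually be detected. This stands, and it confines the concern to rare categories.
- **Low power comes from the sample size, not from the missing interval.** Most non-significant results would still have an interval that includes zero (94% for 1% vs 3%). This also stands: the gain is in what is shown, not in detection.
- **No accept/reject rule exists.** A reader might infer that p > 0.05 will be taken as no difference in harm. No passage says so. The p value is presented in addition to counts and proportions, and safety is also described by SOC and PT, severity, relatedness, duration and listings, with a data monitoring committee reviewing interim data. This stands, but none of these outputs quantifies the uncertainty of the between-arm excess.
- **SAP 6.1 may already supply intervals.** Its wording is not expressly limited to efficacy, so per-arm intervals may be intended. They would still not bound the difference.
- **The reader can derive the interval.** This is true, because the counts are shown. The table layouts are in SAP Module 2, which was not available, but neither document's text asks for a difference or its interval.

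**Conclusion.** The point holds as a cheap improvement. For AE, TEAE, AESI, SAE and PCI proportions, the only planned between-arm inference is a two-sided Fisher p value at 0.05, with no risk difference or interval. At 90 per arm that p value says little about uncommon events: 6 versus 0 is the minimum for significance against no placebo events, and 4 versus 0 (p = 0.12) is compatible with an excess of up to 10.9 points. These two results need only n = 90 per arm and the choice of Newcombe interval. The probabilities of non-significance rest on assumed rates and are illustrations. The concern does not extend to common AEs with a large excess, to the t tests on continuous laboratory and vital-sign changes, or to the primary analysis.

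**What to change.** In SAP 7.10.2, 7.10.3 and 7.10.4, and in Protocol 9.3.2:

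- Present the risk difference, EN3835 minus placebo, with a two-sided 95% confidence interval as the between-arm comparison for any AE, TEAE, AESI, SAE, PCI laboratory values and PCI vital signs.
- Name one interval method in advance, score-type or exact. The 5 versus 0 case shows that the interval and Fisher can fall on different sides of the line, so the text should say which one leads.
- Keep the Fisher p value, if wanted, as descriptive.
- State that p > 0.05 is not evidence of equal risk, and that the upper limit is the largest excess the data do not exclude.

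The cost is SAP and protocol wording and one extra column in the safety tables. No data or subjects are added, and power does not change. The downside is a less favourable-looking safety statement, because wide upper limits will be visible for rare events.
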